Adverse events will be allocated to phases as described in section 5.1.2. Concomitant therapies and procedures will be allocated to phases and (sub)periods as described in section 3.3.2. All other assessments will be allocated to phases and (sub)periods based on the assessment date/time. In case of (partially) missing date/time fields disabling allocation of an assessment to phases or (sub)periods, information from the visit label, time point label and the protocol schedule of activities will be used to allocate to the correct phase.

For efficacy assessments without time part, an assessment on the day of switch from observation phase to treatment phase will be considered as part of the treatment phase. Likewise, an assessment on the day of switch from treatment period 1 to treatment period 2 will be considered as part of treatment period 2.

2.2.2 *Baseline and change from baseline*

Study baseline is defined as the first available and nonmissing value at the baseline visit (scheduled or unscheduled) in ARGX-113-2010. This value corresponds with the value at the EoTP visit in ARGX-113-2009 (and is copied over into the database of ARGX-113-2010 at SDTM level).

Change from baseline is defined as:

- Change from baseline at time point t = value at time point t – baseline value.

Percentage change from baseline at time point t is defined as follows:

- When baseline value is not zero: $100 * ((\text{value at time point } t - \text{baseline value}) / \text{baseline value})$
- When both baseline value and value at time point t are zero: 0
- When baseline value is zero and value at time point t is not zero: not calculated

For immunogenicity assessments, the study baseline selection will be performed by sample (not by parameter) in order to keep the ADA and NAb results of a sample together. Furthermore, values resulting in an unevaluable ADA status are given the lowest priority when the selection is made.

For evaluation of PD parameters, a treatment period-specific baseline (TPnB) will be defined:

	Statistical Analysis Plan	
ARGX-113-2010	Final analysis	Final 1.0 of 29APR2025

- For a treatment period, TPnB is the last available and non-missing value prior to the first IMP administration in the treatment period. Assessments on day 1 of a treatment period without time collection or with time information exactly equal to the time of first IMP administration and which are planned predose will be considered as predose.

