2.3 IMPUTATION AND ROUNDING RULES

2.3.1 Missing values

No imputation will be done of missing values (i.e., observed cases analysis).

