2.4 PRESENTATION OF RESULTS

2.4.1 Calculation of descriptive statistics and percentages

Descriptive statistics for continuous variables will include the number of nonmissing observations, arithmetic mean, standard deviation (SD), standard error (SE), median, minimum, Q1, Q3 and maximum.

Descriptive statistics for immunogenicity titer values will also include geometric mean (GM) and geometric standard deviation (GSD).

Mean, median, Q1, Q3, GM and GSD will be presented with one more decimal place than the reported values. SE and SD will be presented with two more decimal places than the reported values. Minimum and maximum will be presented with the same number of decimal places as the reported values.

Event-type safety data will be summarized by presenting the number and percentage of participants with an event, and the number of events. The denominator will be all participants in the PAS.

	Statistical Analysis Plan	
ARGX-113-2010	Final analysis	Final 1.0 of 29APR2025

For frequency tabulations and cross-tabulations, the denominator will be the number of participants with nonmissing values in the PAS. For tables where results are shown by analysis visit, the denominator will be the number of participants with nonmissing values in the PAS per analysis visit. For cross-tabulations of postbaseline results versus study baseline results, a ‘missing’ category will be shown for baseline results, if applicable, and included in the calculations of percentages.

Percentages will be presented with one decimal place.

	Statistical Analysis Plan	
ARGX-113-2010	Final analysis	Final 1.0 of 29APR2025

2.4.2 *Presentation of treatments*

The following treatment arm label will be used in displays in the ROL analysis set:

- Total

The following treatment arm label will be used in displays in the SAF analysis set:

- Total Efgartigimod PH20 SC

2.4.3 *Ordering in tables, listings, and figures*

In tables showing several parameters, each parameter will begin on a new page and parameters will be sorted alphabetically, within the parameter category if applicable.

Listings will be ordered by participant identifier and, if applicable, by phase/period/subperiod, analysis visit, and time point, unless specified otherwise.

	Statistical Analysis Plan	
ARGX-113-2010	Final analysis	Final 1.0 of 29APR2025

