- 9) Time to relapse:
 - Start date is the first day with status CDA, CR or PR in the treatment period (or observation phase)
 - End date is:
 - the start date of first relapse after having or achieving CDA, CR or PR
 - the end date of the study (end date of last phase), if no relapse
 - Time to relapse (in days) = end date - start date + 1
- 10) For participants with relapse, severity of (first) relapse will be calculated as the BPDAl total score at the onset of relapse (use the first available nonmissing BPDAl total score in the interval of relapse) minus the BPDAl total score at the preceding visit (use the most recent preceding visit for which a nonmissing BPDAl total score is available). Severity of relapse will be categorized as <0 , $0- <10$, $10- <20$, $20- <30$, or >30 .

	Statistical Analysis Plan	
ARGX-113-2010	Final analysis	Final 1.0 of 29APR2025

The following endpoints will be derived **overall**:

- 11) Changes and percent changes from study baseline will be calculated for BPDAI activity and total score.
- 12) Changes from study baseline will be calculated for itch NRS 24-hour average and worst scores.
- 13) C-GTI: Composite Glucocorticoid Toxicity Index comprises the Aggregate Improvement Score (AIS) and the Cumulative Worsening Score (CWS). Details of AIS and CWS derivations are specified in appendix 9.1.
- 14) A total ABQOL score is calculated as the sum of all 17 items score 0 to 3 with higher score indicating worse condition. Missing items are imputed with the average score of the present items if at least half (9) of the items are present. The total score is rounded to the highest integer.
- 15) Changes from study baseline will be calculated for EQ-5D-5L VAS score, DLQI score and total ABQOL score.

4.1.3 *Presentation of results*

Efficacy results will be presented for the ROL analysis set, unless mentioned otherwise. For tables by analysis visit, only the study baseline and last assessment analysis visits will be shown. Other analysis visits will be included in listings.

A frequency tabulation will be created for the number and percentage of participants who achieved CROff at least once during the study (i.e., in any treatment period). The table will also present the number of participants who are evaluable for the endpoint at least once during the study. This number will serve as denominator for the percentage calculation. This table will be based on the SAF analysis set.

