Similar frequency tabulations will be created for the number and percentage of participants who achieved:

- CR/PROff
- CRmin
- Treatment failure

Similar frequency tabulations, based on the ROL analysis set, will be created for:

- CROff without IMP
- CR/PROff without IMP
- Relapse

Duration of sustained remission and time to relapse will be descriptively presented with median times, quantiles and number and percentage of censored observations and observations with event. Only the participant's first evaluation during the study will be included as observation.

Duration of sustained remission will be presented for the SAF analysis set.

A frequency tabulation will be created for categorized severity of relapse, for the participant's first relapse during the study.

	Statistical Analysis Plan	
ARGX-113-2010	Final analysis	Final 1.0 of 29APR2025

Descriptive statistics will present the actual values, changes and percent changes from study baseline of the BPDAl activity and total scores per analysis visit (baseline and last assessment).

Frequency tabulations will be provided for the outcome of IGA-BP per analysis visit (baseline and last assessment). Additionally, cumulative percentages (starting with the best outcome result) will be calculated.

Descriptive statistics will present the actual values and changes from study baseline of the itch NRS 24-hour average and worst scores per analysis visit (baseline and last assessment).

Descriptive statistics will be provided for the C-GTI scores AIS and CWS at the last assessment.

Frequency tabulations will be provided for the outcomes of the ABQOL (17 items), EQ-5D-5L (5 dimensions) and DLQI (10 items), similar to the frequency tabulations of the IGA-BP outcomes. Descriptive statistics on absolute values and changes from study baseline for EQ-5D-5L VAS score, DLQI score and Total ABQOL score will be calculated per analysis visit (baseline and last assessment), similar to the descriptive statistics of the itch NRS scores.

Listings will be created for:

- Disease status, including the derived response variables (CROff, CR/PROff, CRmin, etc.)
- Duration of sustained remission and time to relapse, including the reason for censoring (if applicable) and the severity of relapse
- Lesion assessments
- BPDAl assessments
- IGA-BP assessments
- Itch NRS assessment
- Calculated C-GTI scores and complementary GTI specific list (GTI-SL)
- ABQOL, EQ-5D-5L and DLQI data

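### In the BPDAI percent-change rows, participants who start at 0 are kept if they stay at 0 and dropped if they worsen, so inclusion depends on outcome

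*SAP*

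**What the plan says.** SAP 2.2.2 gives three branches for percent change. With a non-zero baseline the usual ratio is used. With a zero baseline there are two cases: "When both baseline value and value at time point t are zero: 0", and "When baseline value is zero and value at time point t is not zero: not calculated".

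SAP 4.1.2, item 11, applies percent change to one efficacy instrument: "Changes and percent changes from study baseline will be calculated for BPDAI activity and total score". The itch and quality-of-life scores (items 12 and 15) get absolute change only. SAP 4.1.3 tabulates actual values, changes and percent changes together, at baseline and last assessment.

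SAP 2.3.1 rules out imputation. Under SAP 2.4.1, "Descriptive statistics for continuous variables will include the number of nonmissing observations". A percent change that is not calculated therefore leaves the summary.

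On the baseline, SAP 2.2.2 states: "This value corresponds with the value at the EoTP visit in ARGX-113-2009". It is thus measured at the end of the antecedent study.

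**The concern.** Two participants with the same baseline of 0 are treated differently according to what happens later. One who stays at 0 is summarised as no change; one who rises above 0 is not summarised. The Protocol's Definitions of Terms treats a BPDAI activity score of 0 as the healed state, so any other value after 0 is a worsening. Every baseline-zero participant kept in the row has not worsened, and every one dropped has.

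Zero baselines are foreseeable. Complete remission is one of the baseline disease statuses in SAP 3.2.1, and SAP 4.1.2 makes provision for participants already in complete remission on day 1 of a treatment period. At stake is whether the percent-change row, read alone, gives a fair picture of a score that supports the long-term efficacy and durability objective.

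**Working it through.** The plan states no figure for this quantity, so there is none to reproduce. The check applies the rule to pairs of values, then to an assumed cohort.

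**The rule applied to single pairs (baseline, later)**
- (0, 0): 0%, kept
- (0, 1) and (0, 20): no value, dropped
- (10, 0): -100%
- (10, 20): +100%

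**General form.** Let m be the number with a non-zero baseline, S the sum of their percent changes, z the number with baseline 0, and w the number of those who worsen.
- Mean percent change as planned = S / (m + z - w)
- Mean percent change with inclusion decided by baseline only = S / m

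If S is negative (average improvement among non-zero baselines), the planned mean becomes more negative as w rises. If S is positive, dropping worseners pushes it the other way. The flattering direction therefore requires S < 0.

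**Assumed cohort of 100.** These inputs are illustrative and do not come from the documents. Of the 100, 40 start at 0 and the worseners among them go to 20. The other 60 start at 10; 30 of them go to 0 and 30 stay at 10. So m = 60, z = 40, S = 30 x (-100) = -3000, and their absolute changes sum to 30 x (-10) = -300.

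| Worsening from 0 (w) | n in percent-change row | Mean percent change | Mean absolute change, all 100 |
|---|---|---|---|
| 0 | 100 | -3000/100 = -30.0% | -300/100 = -3.0 |
| 4 | 96 | -3000/96 = -31.25% | (-300 + 80)/100 = -2.2 |
| 10 | 90 | -3000/90 = -33.3% | (-300 + 200)/100 = -1.0 |
| 20 | 80 | -3000/80 = -37.5% | (-300 + 400)/100 = +1.0 |

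The two rows of the same table move in opposite directions.

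**Range over the share at baseline 0**, same assumptions, w going from none to half of the baseline-zero group:
- 20 at 0: S = 40 x (-100) = -4000. Mean percent change goes from -40.0% to -4000/90 = -44.4%; absolute change from -4.0 to (-400 + 200)/100 = -2.0.
- 60 at 0: S = 20 x (-100) = -2000. Mean percent change goes from -20.0% to -2000/70 = -28.6%; absolute change from -2.0 to (-200 + 600)/100 = +4.0.

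**The second, opposing effect.** With inclusion decided by baseline only, the 40-at-0 cohort gives -3000/60 = -50.0% whatever w is. The planned rule gives -30.0% to -37.5%, because the 0-to-0 participants pull the mean towards 0.

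**Comparison within the SAP.** For pharmacodynamics, SAP 4.2.2 excludes treatment periods whose own baseline is below quantification or under 20 RU/mL, whatever follows, and promises a footnote. BPDAI has neither.

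**The case against.** The strongest reply is that percent change from 0 is undefined, so no rule can bring the worseners into this row, and nothing is lost elsewhere. Actual values and absolute changes sit in the same tables and keep these participants. Each statistic carries its own n, so the gap between the change and percent-change rows shows how many were dropped. The listed endpoint is BPDAI activity scores over time, and percent change is only one summary of it. The study is descriptive, with no hypothesis test.

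Most of this stands, and it limits the point to the percent-change rows. It does not rescue them. A difference in n tells the reader neither that everyone missing worsened nor how many 0-to-0 participants are in the mean.

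A reader might infer more than the documents support:
- **That relapse is hidden.** It is not. SAP 4.1.2 evaluates relapse in participants having or achieving control of disease activity, complete remission or partial remission, which includes those who enter clear. Tables 14.2.1.7 to 14.2.1.9 report its frequency, timing and severity.
- **That zero baselines will be common.** The documents give no share.
- **That the planned mean is simply too favourable.** Dropping worseners can flatter it while the 0-to-0 participants dilute it. In the assumed cohort, the proposed rule gives a more favourable-looking figure (-50.0%).
- **That both scores are equally affected.** Protocol 8.2.1.3 records damage separately, and complete remission allows residual pigmentation or skin damage. If the total includes damage, which the documents do not say, fewer totals will be exactly 0.

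**Conclusion.** The concern holds for the percent-change rows of Tables 14.2.1.10 and 14.2.1.11, and only there. Inclusion of baseline-zero participants depends on their outcome, and nothing in the SAP overrides this for BPDAI. That conclusion rests on the text and needs no assumption about frequencies.

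The size does need assumptions. With 20 to 60 of 100 starting at 0 and half of them worsening to 20, the mean percent change shifts by 4.4 to 8.6 points in the favourable direction, while mean absolute change worsens by 2.0 to 6.0 points. If none worsens, the selection effect is nil. This is worth correcting before the tables are run, but it affects no primary endpoint, error rate or sample size.

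**What to change.** In SAP 4.1.2, item 11, state that BPDAI percent change is summarised only for participants with a non-zero study baseline, whatever the later value. Apply this to the activity and total scores separately. Leave actual values and absolute changes as they are, with all participants included; the pharmacodynamic exclusion also removes those rows and should not be copied that far.

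In both tables, add a footnote with the number excluded for a baseline of 0. Add one row for that group: n (%) at 0 and n (%) above 0 at last assessment, with the actual scores of those above 0. Record the change in section 6 of the SAP.

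The cost is a few lines of text and one table row, with no new data. The downside is a smaller n for percent change and a mean that describes only participants with a non-zero baseline, which the footnote should say.

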3. OBJECTIVES, ENDPOINTS, AND ESTIMANDS

Table 4: Study ARGX-113-2010 Objectives and Endpoints

Objectives	Endpoints
Primary	
To assess the long-term safety and tolerability of treatment with efgartigimod PH20 SC in participants with BP	
 • Incidence and severity of treatment-emergent AEs, SAEs, and AESIs • Rate of treatment discontinuation because of safety concerns
Secondary	
To assess the long-term efficacy and durability of response with efgartigimod PH20 SC treatment in participants with BP	
 • Proportions of participants achieving^a: 
 – CR while off OCS for ≥ 8 weeks – CR or PR while off OCS for ≥ 8 weeks – CR while on minimal OCS therapy for ≥ 8 weeks. (Minimal OCS therapy is defined as ≤ 0.10 mg/kg/day of prednisone [or an equivalent dose of another OCS]) – CR while off both OCS and efgartigimod PH20 SC for ≥ 8 weeks^b – CR or PR while off both OCS and efgartigimod PH20 SC for ≥ 8 weeks^b • Duration of sustained remission • Proportion of participants who relapse • Time to relapse • Incidence and severity of relapse • BPDAI activity scores, IGA-BP scores, and itch NRS over time • Rate of treatment failure
Additional secondary	
To evaluate the impact of efgartigimod PH20 SC treatment in reducing long-term glucocorticoid-associated toxicity in participants with BP	GTI-related scores, including the GTI-AIS, GTI-CWS, and GTI-SL over time
To evaluate the impact of efgartigimod PH20 SC treatment on QoL in participants with BP	EQ-5D-5L, DLQI, and ABQoL scores over time
To evaluate the PD and immunogenicity of efgartigimod PH20 SC in participants with BP	
 • Percent change from baseline over time for anti-BP180 and anti-BP230 antibody levels • Incidence and prevalence of ADA against efgartigimod (serum levels)

Objectives	Endpoints
Exploratory	
████████████████████ ████████████████████	██ ████████

^a These endpoint criteria can only be met when participants are off rescue therapy.

^b The endpoint applies only to participants who have stopped receiving efgartigimod PH20 SC before protocol amendment 2 is effective.

No estimands have been defined for this OLE study.

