4. STUDY DESIGN

4.1. Overall Design

This is a phase 3, open-label, prospective, global, multicenter, OLE study.

The total study duration is approximately 56 weeks comprising a treatment period of up to 48 weeks and a follow-up of approximately 8 weeks.

The study population is adult patients with BP who have completed ARGX-113-2009.

At rollover, all participants will receive efgartigimod PH20 SC after this amendment is effective. The treatment allocation of ARGX-113-2009 will remain blinded (refer to Section 6.4).

Participants who received placebo in ARGX-113-2009 and participants who have reinitiated efgartigimod PH20 SC treatment will receive [REDACTED] of efgartigimod PH20 SC [REDACTED] (on days 1 and 8) followed by once-weekly maintenance doses of efgartigimod PH20 SC 1000 mg.

Participants who received efgartigimod PH20 SC in ARGX-113-2009 will continue to receive once-weekly efgartigimod PH20 SC 1000 mg maintenance doses.

In the previous protocol version (v2.0), participants had to stop receiving efgartigimod PH20 SC after achieving CR or PR while off concurrent BP therapy for ≥ 8 weeks. For these participants, reinitiation of efgartigimod PH20 SC treatment will be at the investigator's discretion unless the participant relapses. Participants who relapse will initiate efgartigimod PH20 SC treatment (more details are provided in Section 6.3).

Participants will visit the site at weeks 0 (baseline), 1, 2, 4, and 8. Thereafter, participants will attend site visits every 4 weeks. Participants not receiving efgartigimod PH20 SC will attend site visits every 8 weeks.

The OLE study will remain open in all countries for a maximum of 2 years after completion of ARGX-113-2009.

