5.1. Inclusion Criteria

Participants can be included in the study only if all of the following criteria apply:

1. Has completed the week 36 visit of ARGX-113-2009
2. Is capable of providing signed informed consent, as described in Section 10.1.3, and complying with protocol requirements
3. Agrees to use contraceptive measures consistent with local regulations and the following:
 - a. Male participants (contraceptive measures provided in Section 10.4.2.2)
 - b. WOCBP (defined in Section 10.4.1) must have a negative urine pregnancy test at baseline before receiving IMP. (Section 10.4.2.1)

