9.3. Statistical Analyses

9.3.1. General Considerations

- Descriptive statistical methods will be used to analyze all primary and secondary endpoints. For continuous variables, summaries will include the number of observations (n), mean, SE, 95% CI, median, minimum, and maximum. For categorical variables, summaries will include the number of participants, frequencies, and percentages. No inferential analyses are foreseen.
- AEs will be classified using the latest version of the MedDRA classification system.
- AEs, AESIs, and SAEs will be listed corresponding to MedDRA SOC and PT.
- All AEs will be summarized by relatedness to efgartigimod PH20 SC.
- Any AEs leading to death or discontinuation of efgartigimod PH20 SC will be summarized.
- Multiple occurrences of a single PT in a participant will be counted only once at the maximum severity/grade.
- Laboratory parameters, physical examinations, vital sign measurements, PD, and immunogenicity results will be analyzed descriptively.

The baseline value for ARGX-113-2010 will be the value at the EoTP visit of ARGX-113-2009. All study visits will be recalculated based on actual dates and will be referred to as “analysis

visits” that will be used in the statistical analyses. The rules for calculating the analysis visits and the rules for imputing partial dates or missing dates will be provided in the SAP.

Analyses will not only refer to the baseline of ARGX-113-2010; the baseline value of ARGX-113-2009 may be used for specific analysis as will be outlined in the SAP for this OLE study.

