4.2 PHARMACODYNAMICS

4.2.1 *Available data*

The following PD parameters will be measured:

- ██████████
- Anti-BP180 antibodies and anti-BP230 antibodies

4.2.2 *Derivation rules*

BQL or AQL values will be handled as described in section 2.3.3.

Samples for anti-BP180 antibodies and anti-BP230 antibodies will be diluted until the result falls within the reportable range of [20-200 RU/mL]. For anti-BP180 antibodies:

	Statistical Analysis Plan	
ARGX-113-2010	Final analysis	Final 1.0 of 29APR2025

- The value for analysis will be the result with the lowest dilution factor and with value ≤ 200 RU/mL, multiplied by the dilution factor.
- If the result is < 20 RU/mL, the value for analysis will be imputed by 20 RU/mL, multiplied by the dilution factor.
- If at a dilution factor (D1) the result is above 200 RU/mL, and at the next higher dilution factor (D2) the result is < 20 RU/mL, the value for analysis will be derived as $D1 \times 200$ RU/mL.
- If all the results up to dilution factor 32 are above 200 RU/mL, then the value for analysis will be imputed by 6400 RU/mL (32×200), even if the result at a higher dilution factor gives a value below 6400 RU/mL.
- If the result is above 200 RU/mL in the original non-diluted sample and no higher dilution factors are available, the value for analysis will be imputed by 200 RU/mL.
- Multiplication by the dilution factor will be done at analysis level if not yet done by the lab.

For anti-BP230 antibodies:

- If in the original (non-diluted) sample the result is above 200 RU/mL, then the value for analysis will be imputed by 200 RU/mL, even if the result at a higher dilution factor is ≤ 200 RU/mL.
- If the result in the original sample is < 20 RU/mL, the value for analysis will be imputed by 20 RU/mL.

Changes and percent changes versus TPnB will be calculated. Treatment periods with a TPnB value below the limit of quantification (BLQ) or with a result < 20 RU/mL (for anti-BP180 and anti-BP230 antibodies) will be excluded when presenting the actual values, the changes from TPnB and the percent changes from TPnB. This will be explained by a footnote in the appropriate tables.

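### The PD tables take change in anti-BP180/BP230 from a value that is on-drug for continuing participants and efgartigimod-naive for placebo-arm participants, then pool the two

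*SAP*

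**What the plan says.** The additional secondary PD endpoint in Protocol section 3 is "Percent change from baseline over time for anti-BP180 and anti-BP230 antibody levels". Protocol 9.3.1 sets the baseline: "The baseline value for ARGX-113-2010 will be the value at the EoTP visit of ARGX-113-2009". It then adds that "the baseline value of ARGX-113-2009 may be used for specific analysis as will be outlined in the SAP for this OLE study".

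SAP 2.2.2 defines study baseline in the same way ("This value corresponds with the value at the EoTP visit in ARGX-113-2009") and gives PD its own treatment-period baseline: "TPnB is the last available and non-missing value prior to the first IMP administration in the treatment period". SAP 4.2.2 removes some periods from the summaries of actual values, changes and percent changes alike: "Treatment periods with a TPnB value below the limit of quantification (BLQ) or with a result < 20 RU/mL". A footnote is to explain this.

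The other relevant rules are:
- **Pooling.** SAP 2.1.2 analyses everyone as one group, whichever parent-study arm they came from. SAP 2.4.2 gives the safety set a single column.
- **Time points.** SAP 4.2.3 tabulates only the treatment-period baseline and the last assessment.
- **Last assessment.** SAP 2.2.6 lets follow-up-phase values count as the last PD assessment of the preceding treatment period.
- **Parent baseline.** No SAP section outlines a PD analysis that uses the ARGX-113-2009 baseline.

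**The concern.** Protocol 4.1 says: "Participants who received efgartigimod PH20 SC in ARGX-113-2009 will continue to receive once-weekly efgartigimod PH20 SC 1000 mg maintenance doses". For these people the period 1 baseline (TP1B) already contains the drug effect. Change from it describes whether the effect is maintained. For placebo-arm participants, change from TP1B describes what happens after efgartigimod is started. One pooled percent change mixes these two quantities in proportions set by who rolled over.

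Two further rules add to this. The 20 RU/mL exclusion acts on a post-treatment value in continuers, so those left in the table have the higher on-drug titres. And if the last value comes from follow-up, a continuer is compared from an on-drug start to an off-drug end, which can look like a rise in autoantibody.

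At stake is whether the only tabulated percent change can answer the PD objective.

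**Working it through.** The plan states no sample size, arm mix or expected antibody reduction, so there is no planned figure to reproduce. The check traces the rules and then illustrates them.

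**Step 1. What TP1B is, by group.**
- *Efgartigimod arm, dosed at rollover.* Entry requires "Has completed the week 36 visit of ARGX-113-2009", so TP1B follows up to 36 weeks of drug.
- *Placebo arm.* TP1B is efgartigimod-naive but possibly on oral corticosteroids or rescue therapy (Protocol 1.1, Overall Design).
- *Efgartigimod arm, not on drug at rollover.* This covers those who stopped for rescue (Protocol 4.2), were interrupted (Protocol 5.5) or began in the observation phase (SAP Table 2). TP1B may be off-drug.

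**Step 2. Pooling, on-drug endpoint.** Let f be the share continuing and r the on-drug reduction (both assumed), with continuers flat. Then pooled mean change = (1-f)(-r) + f(0) = -(1-f)r.
- f = 0.5: r = 30%, 50%, 70% gives -15%, -25%, -35%.
- r = 50%: f = 0.3 to 0.7 gives -35% to -15%.
- Geometric mean, f = 0.5 and r = 60%: exp(0.5 × ln 0.4) - 1 = -36.8%, against -60% in new starters.

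**Step 3. Exclusion.** A continuer drops out when the pre-drug level × (1-r) is below 20, that is, when the pre-drug level is below 20/(1-r). The cut-off is 33, 50 and 100 RU/mL for r = 40%, 60% and 80%. At r = 60%, a continuer who began at 40 RU/mL (now 16) is removed, and one who fell from 300 to 120 stays.

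A simulation combined steps 2 and 3. It assumed log-normal pre-drug levels (log-SD 1.0), noise of log-SD 0.3, f = 0.5, values floored at 20, no upper cap and an on-drug endpoint.

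| Pre-drug median (RU/mL), r | Excluded: continuers / new starters | Mean % change as planned | Without exclusion | From parent baseline | Median last value: kept / all |
|---|---|---|---|---|---|
| 50, 40% | 34.9% / 19.0% | -15.4 | -10.1 | -32.2 | 42.7 / 30.0 |
| 50, 60% | 49.9% / 19.0% | -28.4 | -17.5 | -48.5 | 31.3 / 20.0 |
| 100, 40% | 14.6% / 6.2% | -14.0 | -11.8 | -33.4 | 68.6 / 59.9 |
| 100, 60% | 25.3% / 6.2% | -26.5 | -21.4 | -52.7 | 49.2 / 40.0 |
| 200, 40% | 4.2% / 1.4% | -13.0 | -12.3 | -34.0 | 124.8 / 120.4 |
| 200, 60% | 9.3% / 1.4% | -24.9 | -23.0 | -55.0 | 85.7 / 79.9 |

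In every run the exclusion removes more continuers than new starters, raises the median last value and partly offsets the dilution of percent change.

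**Step 4. Off-drug endpoint.** The schedule samples PD at both follow-up visits, 4 and 8 weeks after the end-of-treatment visit. A completer with the second sample therefore has an off-drug last assessment. Take a pre-drug level of 100 and r = 50%, so the on-drug level is 50, and suppose half the fall is regained: 50 + 0.5 × 50 = 75.
- Continuers: 75/50 - 1 = +50%.
- New starters: 75/100 - 1 = -25%.
- Pooled at f = 0.5: +12.5%.

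The sign has changed, so the figures in steps 2 and 3 hold only for an on-drug endpoint.

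**The case against.** The best defence is that the SAP does what the protocol says. Protocol 9.3.1 fixes the rollover value as baseline and only permits the parent-study one. Pooling is stated openly, no estimand is defined and nothing is tested. The 20 RU/mL rule has a reason, since values are floored at 20 and no fall can be seen below that. It is footnoted, and listings show the non-imputed results.

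Much of this stands. There is no protocol–SAP contradiction, change from rollover is a valid maintenance measure, and the exclusion is defensible for percent change. But the floor gives no reason to drop the same periods from the actual values. The listings are not specified to carry the parent-study baseline, so they do not recover the pre-drug comparison for continuers.

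A reader might infer more than the documents support:
- *The estimate is biased towards no effect.* Step 4 shows that the net direction depends on the endpoint and on rebound. The exclusion also works against the dilution.
- *The continuers kept are poor PD responders.* Under a uniform reduction there are none, and exclusion depends only on starting level. What can be said is that higher on-drug titres remain.
- *Placebo-arm values are untreated, so their change is a pure drug effect.* Corticosteroids or rescue therapy may be present and tapering.
- *The whole former efgartigimod arm is on drug at rollover.* Step 1 shows that it is not.

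**Conclusion.** The point holds as a problem of interpretation that should be corrected before the PD tables are produced. The planned percent change combines maintenance in continuers with initiation in placebo-arm participants. It may also mix on-drug and off-drug endpoints, and it leaves unused the parent-study baseline that the protocol allows. The low-baseline exclusion also selects on a post-treatment value in continuers and needlessly thins the actual-value summary.

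The size cannot be established from the documents. With half continuing and continuers flat, the pooled mean at an on-drug endpoint is half the new-starter change. In the simulated scenarios it was -13% to -28%, against -32% to -55% from the parent-study baseline. These figures rest on assumed arm mix, reduction, titre distribution and noise.

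**What to change.** Amend SAP 2.2.2, 2.2.6, 4.2.2 and 4.2.3 as follows:

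1. Show Tables 14.2.3.1 and 14.2.3.2 by parent arm. Show efgartigimod-arm participants not on drug at rollover separately, or footnote them.
2. For efgartigimod-arm participants, add change and percent change from the ARGX-113-2009 baseline. For anti-BP180 and anti-BP230, apply the 20 RU/mL rule to that pre-drug value. Keep change from TP1B as a supportive maintenance row.
3. Tabulate the last on-treatment value separately from the follow-up value.
4. Keep periods with a treatment-period baseline below 20 RU/mL in the actual-value summary, and report by parent arm how many are excluded from percent change.

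The cost is SAP wording, a merge of parent-study baseline antibody values, and smaller groups per column. No error rate is affected, because the analysis is descriptive. The SAP already uses parent arm for evaluability (4.1.2), parent screening height (3.2.2) and copied end-of-treatment values (2.2.2). Parent allocation is blinded only until the ARGX-113-2009 database lock.
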